5.2.1. Data Handling After the Cut-off Date

Data after the cut-off date may not undergo the cleaning process and will not be displayed in any listings or used for summary statistics, statistical analyses or imputations.

5.2.2. Pooling of Centers

In order to provide overall estimates of treatment effects, data will be pooled across centers. The 'center' factor will not be considered in statistical models or for subgroup analyses due to the high number of participating centers in contrast to the anticipated small number of patients randomized/treated at each center.

5.2.3. Presentation of Continuous and Qualitative Variables

Continuous variables will be summarized using descriptive statistics ie, number of non-missing values and number of missing values [ie, n (missing)], mean, median, standard deviation (SD), minimum, maximum and first and third quartile (Q1 and Q3).

Qualitative variables will be summarized by frequency counts and percentages. Unless otherwise specified, the calculation of proportions will include the missing category. Therefore counts of missing observations will be included in the denominator and presented as a separate category.

In case the analysis refers only to certain visits, percentages will be based on the number of patients still present in the study at that visit, unless otherwise specified.

5.2.4. Definition of Study Day

Start day of study treatment is the day of the first dose of study treatment.

The study day for assessments occurring on or after the start of study treatment (eg, adverse event onset, tumor measurement) will be calculated as:

$$\text{Study day} = \text{Date of the assessment/event} - \text{start of study treatment} + 1.$$

The study day for assessments occurring prior to the first dose of study treatment (eg, baseline characteristics, medical history) will be negative and calculated as:

$$\text{Study day} = \text{Date of the assessment/event} - \text{start of study treatment}.$$

The study day will be displayed in all relevant data listings.

5.2.5. Definition of Start of New Anti-cancer Drug Therapy

Start date of new anti-cancer drug therapy is used to determine the end of the on-treatment period (see Section 5.2.7).

The start date of new anti-cancer drug therapy is the earliest start date of anti-cancer drug therapy recorded in the ‘Follow-up Systemic Therapy’ eCRF pages that is after the first dose of study treatment. When start date of anti-cancer drug therapy is missing or partially missing, the imputation rules described in [Section 5.3.3.4](#) should be applied using only data from the ‘Follow-up Systemic Therapy’ eCRF pages.

5.2.6. Definition of Start of New Anti-cancer Therapy

Start date of new anti-cancer therapy (drug, radiation, surgery) is used for censoring in efficacy analyses (see [Section 6.1.2](#) and [Section 6.2.2](#)).

The start date of new anti-cancer therapy is the earliest date after the first dose of study treatment for non-randomized cohorts or after the date of randomization for randomized cohorts amongst the following:

- Start date of anti-cancer drug therapy recorded in the ‘Follow-up Systemic Therapy’ eCRF pages.
- Start date of radiation therapy recorded in ‘Concomitant Radiation Therapy’ with ‘Treatment Type’ not equal to ‘Palliative’.
- Surgery date recorded in ‘Concomitant Surgery’ when “Surgery Outcome” = ‘Resected’ or ‘Partially Resected’.

When start date of anti-cancer therapy is missing or partially missing, the imputation rules described in [Section 5.3.3.4](#) should be applied using ‘Follow-up Systemic Therapy’, ‘Concomitant Radiation Therapy’ and ‘Concomitant Surgery’ eCRF pages.

5.2.7. Definition of On-treatment Period

Safety endpoints will be summarized based on the on-treatment period unless otherwise specified.

On-treatment period is defined as the time from the first dose of study treatment through minimum (30 days + last dose of study treatment, start day of new anti-cancer drug therapy – 1 day).

Safety data collected outside the on-treatment period as described above will be listed and flagged in listings but not summarized.

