30. Follow up period: Patients should be evaluated for serious adverse events up to 60 days after last dose of study treatment. Patients continuing to experience toxicity at this point will continue to be followed at least every 4 weeks until resolution or determination, in the clinical judgment of the Investigator, that no further improvement is expected. Immunogenicity (ADA) samples should be collected beyond 28 days for patients who are positive for ADA (Refer to Footnote 27). During the follow-up phase, Immunogenicity (ADA) samples should be collected at the same time as disease assessments are being performed until ADA levels return to baseline or until the patient enters the survival follow phase. Thereafter, patients whose disease has not progressed at the end of treatment will enter into disease follow-up. During this follow-up period, patients will have disease assessments performed every 16 weeks (± 1 week). Once patients have exhibited disease progression, they will enter into survival follow-up for assessment of survival only. A new anti-cancer therapy will be reported on the CRF. Follow-up for survival will be conducted every 12 weeks (± 4 weeks) for up to 2 years from first dose of study treatment for the last enrolled patient (telephone calls acceptable).
31. For patients continuing on study beyond 8 cycles of therapy, continued treatment will be on a reduced visit schedule (Day 1 of each cycle), or as clinically indicated, until disease progression, loss of clinical benefit, unacceptable toxicity, or withdrawal of consent up to a maximum of 2 years from the first dose of study drug.

CCI

Table 3. Schedule of Activities: Portion B (PF-05082566 + Rituximab) Assessments (Dose Escalation Only)

Protocol Activity (Cycle Day relative to PF-05082566 dosing)	Screen ¹	CYCLE 1						CYCLE ≥2-8 ³⁵				>Cycle 8 ^{23,26,35}	End of Treatment ³²	Follow up ³³
	Within 28 days prior to enrollment	Day (-7) ³⁴	Day (0)	Day 1	Day 7	Day 14	Day 22	Day 1 (± 2)	Day 8 (± 2)	Day 15 (± 2)	Day 22 (± 2)	Day 1 (± 2)		
Visit Window														
Informed Consent ²	X													
Tumor History ³	X													
Medical History ⁴	X													
Physical Examination ⁵	X	X		X				X				X	X	
ECOG Performance Status ⁶	X	X		X				X					X	
Baseline Signs and Symptoms ⁷	X													
Vital Signs (BP, pulse, and body temperature) ⁸	X	X	X	X	X	X	X	X				X	X	
Safety Labs/Measurements														
12-Lead ECG ⁹	X	X		X		X		X				X	X	
Hematology ¹⁰	X	X	X	X	X	X	X	X	X	X	X	X	X	

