Baseline Signs and Symptoms ⁹	X								
Vital Signs (BP, pulse, body temperature for Portion B) ¹⁰	X	X	X	X	X	X	X	X	
Neurological Examination (Portion B) ²⁹	As clinically indicated								
Central histopathology review of FL diagnosis (Portion B) ³⁰	X								
Safety Labs /Measurements									
12-Lead ECG ¹¹	X	X		X			X (C2, C3, C4)	X	
Hematology and Blood Chemistry ¹²	X	X	X	X	X	X	X	X	
Coagulation ¹³	X	X	X	X	X	X	X	X	
Urinalysis ¹⁴	X			X				X	
Pregnancy test ¹⁴	X			X			X	X	
Hepatitis B and C testing [hepatitis B surface antigen and core antibody; anti-hepatitis C antibody]	X								
Endocrine function assessment ¹⁶	X						X	X	
LVEF assessment ¹⁷	X			As clinically indicated					
Registration and Treatment									
Registration ¹⁸		X		X					
Administration of PF-05082566 ¹⁹				X			X		

2. End of Treatment: To be performed approximately 28 days after the last dose of study treatment. Obtain these assessments if not completed during the previous week (during the previous 6 weeks for tumor assessments).
3. Follow-up period: Patients should be evaluated for adverse events up to 60 days after last dose of study treatment. Patients continuing to experience toxicity at this point following discontinuation of treatment will continue to be followed at least every 4 weeks until resolution or determination, in the clinical judgment of the Investigator, that no further improvement is expected. Patients whose disease has not progressed at the end of treatment will enter into disease follow-up. During this follow-up period, patients will have disease assessments performed every 16 weeks (± 1 week). Once patients have exhibited disease progression, they will enter into survival follow-up for assessment of survival only. Any new anti-cancer therapy will be reported on the CRF. Survival follow-up will be conducted every 12 weeks (± 4 weeks) for survival status and subsequent anti-cancer treatment, up to 2 years from the first dose of study treatment for the last treated patient (for the non-randomized cohorts) or from the randomization date for the last randomized patient (for the randomized cohorts). Telephone calls are acceptable.

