23. AE Assessment: AEs should be documented and recorded at each visit using NCI CTCAE version 4.03. Patients must be followed for AEs for 28 days after the last treatment administration or until all drug related toxicities have resolved, whichever is later; or earlier than 28 days should the patient commence another anticancer therapy in the meantime. For SAEs, the active reporting period to Pfizer or its designated representative begins from the time that the patient provides informed consent, which is obtained prior to the patient’s participation in the study, ie, prior to undergoing any study related procedure and/or receiving investigational product, through and including 60 calendar days after the last administration of the investigational product. SAEs experienced by a patient after the active reporting period has ended should be reported to

the Sponsor if the investigator becomes aware of them; at a minimum, all SAEs that the investigator believes have at least a reasonable possibility of being related to study drug are to be reported to the Sponsor.

24. Concomitant Medications: All concomitant medications including supportive care drugs (eg, Anti emetic treatment and prophylaxis), and the drugs used to treat AEs or chronic diseases should be recorded in the CRF.

CCI

30. Central Histopathology Review of FL Diagnosis (Portion B only): Slides from the archival (tissue collected within the last 6 months) OR a baseline (tissue collected *de novo* during the screening period prior to the first dose of PF-05082566) tumor biopsy must be sent to a central pathology laboratory for independent review. Confirmation of the FL diagnosis is not required for patient enrollment. See the study manual for more details.

CCI

32. Bone marrow (BM) biopsy or aspirate: Required for patients with potential CR by radiological assessments to determine the response category.

Table 6. Schedule of Activities: Portion A (PF-05082566 Alone: Dose Expansion Cohorts): Pharmacokinetic assessments

Assessments [(±) 2 days for cycles >1]	Cycle 1			Cycle 2 and 3	Cycle 4			Cycle ≥5	End of Treatment	
	Day 1	Day 7	Day 14	Day 1	Day 1	Day 7	Day 14	Day 1		
Blood for PF-05082566 PK ¹	X	X	X	X	X	X	X	X (every 4 cycles)	X	
Blood for Immunogenicity (ADA) testing ²	X			X	X			X (every 4 cycles)	X	

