8.2. Reporting Period

For SAEs, the active reporting period to Pfizer or its designated representative begins from the time that the patient provides informed consent, which is obtained prior to the patient's participation in the study, ie, prior to undergoing any study-related procedure and/or receiving investigational product, through and including 60 calendar days after the last administration of the investigational product. SAEs occurring to a patient after the active reporting period has ended should be reported to the Sponsor if the investigator becomes aware of them; at a minimum, all SAEs that the investigator believes have at least a reasonable possibility of being related to investigational product are to be reported to the Sponsor.

AEs (serious and non-serious) should be recorded on the case report form (CRF) from the time the patient has taken at least one dose of investigational product through the patient's last visit.

If a patient begins a new anticancer therapy, the AE reporting period for non-serious AEs ends at the time the new treatment is started. Death must be reported if it occurs during the SAE reporting period after the last dose of investigational product, irrespective of any intervening treatment.

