6.6.3. Serious Adverse Events

The frequency (number and percentage) of patients with each of the following will be presented for treatment-emergent SAEs by treatment group:

- SAEs by SOC and PT;
- Related SAEs by SOC and PT.

The listings of all SAEs will also be provided with the relevant information with a flag for SAEs with onset outside of the on-treatment period.

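### SAEs starting 31–60 days after the last dose are collected and listed but appear in no adverse-event or SAE incidence table; only deaths are tabulated to day 60

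*SAP*

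**What the plan says.** **Collection.** Protocol Section 8.2 runs active SAE reporting from consent "through and including 60 calendar days after the last administration of the investigational product", and footnote 23 of Table 5 repeats this for the expansion cohorts. Section 8.2 also has AEs recorded on the CRF from the first "dose of investigational product through the patient's last visit". It lets new anticancer therapy end the reporting period for non-serious AEs only.

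**Analysis.** SAP Sections 3.8.1 and 5.2.7 end the on-treatment period at the earlier of last dose plus 30 days and the day before new anti-cancer drug therapy. For anything later, Section 5.2.7 says: "Safety data collected outside the on-treatment period as described above will be listed and flagged in listings but not summarized". SAP 6.6.1 bases the AE analyses on treatment-emergent events by default. In SAP 6.6.3 the SAE and related-SAE frequencies "will be presented for treatment-emergent SAEs by treatment group"; the SAE listings cover all SAEs, with a flag for onset outside the period. SAP 6.6.2 tabulates all deaths, deaths within 30 days and deaths within 60 days, with the primary reason.

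**The protocol's own analysis plan.** Section 9.6.2 treats an event as treatment-emergent if it starts or worsens after the first dose, with no end day. It summarises AEs and SAEs over the whole study period as well as by cycle.

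**Table 5 on AE follow-up.** Footnote 3: "Patients should be evaluated for adverse events up to 60 days after last dose of study treatment". Footnote 23: "Patients must be followed for AEs for 28 days after the last treatment administration or until all drug related toxicities have resolved, whichever is later". That period is cut short if another anticancer therapy starts.

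**The concern.** The protocol asks sites for SAEs over 60 days after treatment, and the SAP counts them over 30. The second half of that window is the part in which a delayed event would show, and it reaches the reader only as flagged lines in a listing. Dosing is every 4 weeks, so 30 days is about one dosing interval. The protocol itself names endocrine and hepatic events for careful monitoring (Section 7.1.2.1) and reports enterocolitis and pneumonitis among the few SAEs judged related so far (Section 1.4).

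At stake is whether the headline SAE and related-SAE percentages by dose describe what was collected. Groups are small: about 20 melanoma patients are planned per expansion dose (protocol Section 9.3). With a denominator of 20, one uncounted patient with a related SAE is 1/20 = 5 percentage points, and proportionally less in a larger group.

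**Working it through.** **1. Windows after the last dose, side by side**

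| Item | End of window | Source |
|---|---|---|
| SAE collection | day 60, regardless of new therapy | Protocol 8.2; Table 5 fn 23 |
| AE and SAE incidence tables | day 30, or day before new anti-cancer drug therapy | SAP 5.2.7, 6.6.1, 6.6.3 |
| Death table | day 30, day 60, and all deaths | SAP 6.6.2 |
| SAE listings | no end, late onset flagged | SAP 6.6.3 |
| Protocol AE/SAE summaries | entire study period | Protocol 9.6.2 |

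**2. Following single events through the plan**

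- *Non-fatal related SAE, day 40, no new therapy.* It is collected (40 ≤ 60). It is not treatment-emergent (40 > 30), so it is absent from the 6.6.1 and 6.6.3 tables. It is listed with a flag.
- *Non-fatal SAE, day 20, new drug therapy from day 15.* It is still collected, because only non-serious reporting stops at new therapy. The on-treatment period ended on day 14, so the event is again listed but not counted.
- *SAE starting day 40 and fatal by day 60.* It is counted in the death table with a reason, but not among treatment-emergent events leading to death by system organ class and preferred term.

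**3. Size in time**

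Uncovered days: 60 − 30 = 30, and 30/60 = 50% of the post-treatment SAE window. This is a minimum, since earlier new drug therapy shortens the tabulated part.

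As a share of time from first dose, let T be the days from first to last dose, so the share is 30/(T + 60). The second dose falls on Day 29 (protocol Section 3.3.1), so two on-schedule doses give T = 28.

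| Treatment | T (days) | Share untabulated |
|---|---|---|
| 1 dose | 0 | 30/60 = 50% |
| 2 doses | 28 | 30/88 = 34% |
| 3 doses | 56 | 30/116 = 26% |
| T of 168 days | 168 | 30/228 = 13% |
| about 2 years | 728 | 30/788 = 4% |

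**4. Size in events**

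This cannot be computed: the documents give no overall SAE rate and no onset times. As an illustration only, assume a constant daily SAE hazard h after the last dose, with monthly risk m and h = −ln(1 − m)/30.4375. The share of first post-treatment SAEs (those within 60 days) with onset on days 31–60 is (e^(−30h) − e^(−60h))/(1 − e^(−60h)). For m = 2%, 5%, 10%, 20% and 30% this gives 49.5%, 48.7%, 47.4%, 44.5% and 41.3%.

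**5. Table 5, footnotes 3 and 23**

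For SAEs both footnotes are compatible with 60 days. For non-serious AEs, footnote 3 gives 60 days, while footnote 23 gives 28 days or until drug-related toxicity resolves, if later. Tables 3 and 4 carry the same pair of statements (footnotes 33 and 21). The matching footnote 30 of Table 1 is worded for serious events only: "Patients should be evaluated for serious adverse events up to 60 days after last dose of study treatment".

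**The case against.** The strongest reply is that a 30-day window is an ordinary choice and nothing is hidden. The End of Treatment visit is about 28 days after the last dose, so the window fits the schedule, and the same window governs laboratory, vital-sign and ECG summaries. Both documents allow the SAP to modify protocol plans. Late SAEs stay in the listings, and late deaths are tabulated. A longer window also admits events caused by progression or later therapy.

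Most of this stands. It justifies keeping the 30-day treatment-emergent tables and shows that the SAP's departure from protocol Section 9.6.2 is permitted. It does not explain why non-fatal SAEs, collected to day 60, get no count to that day when deaths do. The SAP gives no reason for the narrowing.

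Three stronger readings are tempting, and the documents do not support them:

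- *Late SAEs are missing from every safety table or lost from the report.* SAP 6.6.2 counts fatal cases, including a toxicity category for the reason, and SAP 6.6.3 lists all SAEs.
- *The Table 5 conflict causes the omission.* The SAP window causes it. The footnotes agree on SAEs, and footnote 23's 28 days is extended while drug-related toxicity persists.
- *The RP2D will be chosen on truncated data.* Protocol Section 3.6 bases the choice on the primary and secondary endpoints, and Section 9.7 has an internal team reviewing individual as well as summary data. Nothing ties the decision to the 30-day tables.

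**Conclusion.** The point holds as a reporting gap. SAEs with onset on days 31–60 after the last dose, or sooner if new anti-cancer drug therapy has begun, are collected and listed but enter no AE or SAE incidence table. The untabulated part is half of the post-treatment SAE window. From first dose it ranges from 50% of observation time after one dose to about 4% at two years. These are shares of time, not of events; the event shares in the working rest on an assumed constant hazard.

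The time figures assume on-schedule dosing, no earlier new therapy, and the same last-dose date in both documents. In Portion B that last assumption can fail for a patient who stops early. The SAP takes the later of the two drugs' last doses, the protocol counts from the last investigational product, and Section 5 says rituximab has that status only in some countries.

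The change is worthwhile because it is cheap and uses data already in hand. A change to the treatment-emergent window itself is not needed. The Table 5 wording is a separate, smaller matter confined to non-serious AEs.

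**What to change.** 1. In SAP 6.6.3, add SAE and related-SAE tables by system organ class and preferred term through 60 days after the last dose, regardless of new anti-cancer therapy. Keep the present 30-day treatment-emergent tables beside them.
2. In SAP 5.2.7, name these tables as an exception to the listing-only rule, and give the reason for the 30-day window in light of protocol Section 9.6.2.
3. Separately, reconcile footnotes 3 and 23 of Table 5 so that sites have one stated follow-up period for non-serious AEs. Which period applies is for the sponsor to settle.

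The cost is two tables and two wording changes, with no new data collection. The small downside is that some SAEs in the longer window will reflect progression or later therapy; the related-SAE table and the retained 30-day tables help the reader separate these.

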5.2.8. Standard Derivations and Reporting Conventions

The following conversion factors will be used to convert days into weeks, months or years:
1 week = 7 days, 1 month = 30.4375 days, 1 year = 365.25 days.

Demographics and physical measurements:

- Age [years]:
 - $(\text{date of given informed consent} - \text{date of birth} + 1) / 365.25$
 - In case of missing day, day only: Age [years]: $(\text{year/month of given informed consent} - \text{year/month of birth})$
 - In case only year of birth is given: Age [years]: $(\text{year of given informed consent} - \text{year of birth})$

The integer part of the calculated age will be used for reporting purposes.

- $\text{BMI (kg/m}^2\text{)} = \text{weight (kg)} / [\text{height (m)}]^2$
- $\text{BSA (m}^2\text{)} = ([\text{height (cm)} \times \text{weight (kg)}] / 3600)^{0.5}$

For reporting conventions, mean and median should generally be displayed one more decimal place than the raw data and standard deviation should be displayed to two more decimal places than the raw data. Percentages will be reported to one decimal place. The rounding will be performed to closest integer / first decimal using the common mid-point between the two consecutive values. E.g., 5.1 to 5.4 will be rounded to an integer of 5, and 5.5 to 5.9 will be rounded to an integer of 6.

5.2.9. Unscheduled Visits

Generally, data collected at unscheduled visits will be included and analyzed for both safety and efficacy analyses in the same fashion as the data collected at scheduled visits except where otherwise noted in the sections that follow. Descriptive statistics (mean, SD, median, minimum, maximum, quartiles) by nominal visit or time point for safety endpoints such as laboratory measurements, ECGs and vital signs will include only data from scheduled visits.

5.2.10. Adequate Baseline Tumor Assessment

Adequate baseline is defined using the following criteria:

- All baseline assessments must be within 28 days prior to and including ‘start date’.
- All documented lesions must have non-missing assessments (ie, non-missing measurements for target lesions (for patients with solid tumor) or index lesions (for patients with NHL) and non-missing lesions status at baseline for non-target lesions (for patients with solid tumor) or non-index lesions (for patients with NHL)).

- Computerized tomography (CT) or magnetic resonance imaging (MRI) is required at baseline and may include chest, abdomen and pelvis. Brain scans will be performed at baseline for patients with CNS disease or if disease is suspected, and on study as appropriate to follow disease. Baseline CNS imaging is not required unless to confirm stability of existing CNS metastases or for symptomatic patients to rule out CNS metastases. Bone scans will be performed at baseline if disease is suspected only for patients enrolled in Portion A, and on study as appropriate to follow disease.

